	
 - WHO index≤ 2 - Life expectancy≥ 3 months - No extra-hepatic disease, except pulmonary nodules if number≤ 3 and size < 10 mm each - Hepatic Involvement < 60 - Primary tumor resected or in place - No prior chemotherapy for metastases (except peri-operative chemotherapy, if the last cycle was given at least 12 months ago) - Adjuvant chemotherapy after resection of the primary site allowed if the last cycle was administered at least 12 months ago - Normal liver function: total bilirubin ≤ 1.5N, AST≤ 5N, ALT ≤ 5N and PAL≤ 5N. - TP ≥ 60% - Adequate hematologic function: PNN ≥ 1500/mm³ , platelets ≥ 100,000/mm³ , Hb ≥ 9g/dL - Good renal function: creatinine clearance ≥ 60 mL/min - No cardiac dysfunction: no cardiovascular events in the past 6 months or no NYHA ≥ 2
Non-inclusion criteria	
 - Patient eligible for curative treatment (resection and/or radiofrequency ablation) according to a PCR (including the opinion of a liver surgeon) - Pregnant or breastfeeding women or patients of either sex of childbearing age who are not using an adequate method of contraception (see section V. 4) - Previous cancer, except for non-melanoma skin cancers and curatively treated cervical in situ cancers. Other curatively treated cancers are allowed provided they have not recurred for more than 5 years - Peripheral neuropathy - Inflammatory bowel diseases - Intestinal occlusion - Chronic liver disease (viral, alcoholic or metabolic) - Immunodeficiency syndromes (history of transplantation, HIV

	
infection)
 
 - Known contraindications to 5FU, oxaliplatin, folinic acid, irinotecan or contrast media - Patient with known contraindication to liver embolization procedures: 
 Presence of bilio-digestive anastomoses or biliary prosthesis Cruciate or tumor thrombosis of the portal vein - Patient who for psychological, social, family or geographical reasons could not be followed regularly - Legal incapacity (persons deprived of liberty or under guardianship) - Patient not affiliated to a social security system - Concurrent participation in another study investigating the effect of a treatment until 4 weeks after the end of this study.

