Planned study period	
Expected start date of inclusion: April 2013
 
Expected completion date of inclusion: April 2016
 
Expected completion date: July 2018

I. OBJECTIVES OF THE TRIAL

I.1 Main objective

Evaluate the investigator-assessed 9-month progression-free survival rate (according to RECIST 1.1 criteria).

I.2 Secondary objectives

Tolerance to treatment

Response rate according to RECIST 1.1 criteria at 9 months

Response rate according to EASL criteria, assessed at 9 months, by centralized review

Hepatic progression-free survival according to RECIST 1.1

Overall survival

Progression-free survival

Secondary resection rate

Evolution of tumor marker levels

II. PATIENT SELECTION

II.1 Inclusion criteria

Inclusion in the study requires that all of the inclusion criteria listed below be met:

- Histologically proven colorectal adenocarcinoma
- Radiologically or histologically proven liver metastases
- At least one measurable liver lesion according to RECIST v1.1 criteria
- Age \geq 18 years
- WHO Index \leq 2
- Life expectancy \geq 3 months
- No extra-hepatic disease, except pulmonary nodules if number \leq 3 and size $<$ 10 mm each
- Hepatic invasion $<$ 60%.
- Primary tumor resected or in place
- No prior chemotherapy for metastases (except peri-operative chemotherapy, if the last cycle was given at least 12 months ago)
- Adjuvant chemotherapy after resection of the primary site allowed if the last cycle was administered at least 12 months ago
- Normal liver function: total bilirubin \leq 1.5N, AST \leq 5N, ALT \leq 5N and PAL \leq 5N.

- TP \geq 60%
- Adequate hematologic function: PNN \geq 1500/mm³ , platelets \geq 100,000/mm³ , Hb \geq 9g/dL
- Good renal function: creatinine clearance \geq 60 mL/min
- No cardiac dysfunction: no cardiovascular events in the past 6 months or no NYHA \geq 2.

II.2 Non-inclusion criteria

Inclusion in the study requires that none of the non-inclusion criteria listed below are present:

- Patient eligible for curative treatment (resection and/or radiofrequency ablation) as determined by the PCR (including the opinion of a liver surgeon)
- Pregnant or breastfeeding women or patients of either sex of childbearing age who are not using an adequate method of contraception (see section V. 4)
- Previous cancer, except for non-melanoma skin cancers and curatively treated cervical in situ cancers. Other curatively treated cancers are allowed provided they have not recurred for more than 5 years

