- Peripheral neuropathy
- Inflammatory bowel diseases
- Intestinal occlusion
- Chronic liver disease (viral, alcoholic or metabolic)
- Immunodeficiency syndromes (transplant history, HIV infection)
- Known contraindications to 5FU, oxaliplatin, folinic acid, irinotecan or contrast media
- Patient with known contraindication to liver embolization procedures:
 - Presence of bilio-digestive anastomoses or biliary prosthesis
 - Cruciate or tumor thrombosis of the portal vein
- Patient who for psychological, social, family or geographical reasons could not be followed regularly
- Legal incapacity (persons deprived of liberty or under guardianship)
- Patient not affiliated with a social security plan.
- Concurrent participation in another study investigating the effect of a treatment until 4 weeks after the end of this study.

III. PRE-INCLUSION ASSESSMENT

To be performed within 21 days prior to treatment and before inclusion:

- Thoracoabdomino-pelvic CT scan, documenting at least one measurable liver lesion
- Hepatic MRI
- PET scan strongly recommended before inclusion.

Remember to keep the radiology CDs in the patient's file; the ARC FFCD will make a copy of these imaging studies.

To be completed within 14 days prior to inclusion:

- Complete clinical examination including: weight, height, vital signs, WHO index, pain assessment (VAS)
- Medical history
- Description of the disease
- Biological workup consisting of measurements of hematological, nephrological and hepatic parameters: CBC/platelets, blood ionogram, creatinine, albumin, transaminases (AST, ALT), alkaline phosphatases (ALP), total and conjugated bilirubin, PT, APTT, fibrinogen level
- Determination of lipase
- ACE and CA 19-9 assay
- KRAS status will be determined at each center but not routinely at inclusion
- **Fasting** sample for patients participating in the 'lipid' translational study; don't forget to perform it (according to the corresponding section, p25).

IV. INCLUSION

After the patient has signed the clinical consent form (Appendix 1) and the results of the examinations necessary for inclusion in the study have been verified, the patient can be included. For centers participating in the associated 'lipid' study, the specific information and consent form (Appendix 2) must be proposed.

[figure not shown]

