Primary prophylaxis with G-CSF should be used until all chemoembolization procedures have been completed and then left to the discretion of the investigator thereafter. The choice of G-CSF is left to the discretion of the investigator.

The following prophylactic treatments are recommended:

- **Prophylactic treatment to prevent renal failure:** IV hydration started the day before chemoembolization and continued until day 2, with a 2,000-mL bag per day (1,000 mL of saline + 1,000 mL of 5% glucose).
- **Prophylactic treatment of gastric toxicities:** esomeprazole 80 mg at D0, D1 and D2, infusion (oral possible for D1 and 2).
- **Prophylactic treatment of nausea and vomiting:** ondansetron 8 mg or granisetron 3 mg, before chemoembolization and 8 mg 6h after (at D0) and prednisolone 40 mg twice a day at D0, D1; then 40 mg/d at D2, D3, D4, D5
- **Prophylactic treatment of pain:**
Ideally, self-administration of level 3 analgesics by PCA (Patient Control Analgesia) is implemented. The injected preparation is oxycodone 2 mg, injected by a pump with a

refractory period of 3 min and with a maximum dose of 20 mg per 4h. This PCA will be maintained for 12 hours after chemoembolization.

Otherwise, 5 to 10 mg of morphine, 30 minutes before and 6 hours after chemoembolization. This prophylaxis is given as an indication and can be modified at the investigator's discretion.

Intra-arterial infusion of 1-3 mL of 1% lidocaine immediately prior to chemoembolization with DEBIRI.

- **Prophylactic treatment of infections:** 2000 mg of cefazolin twice a day, at D0, D1 and D2.

V.3 Simplified FOLFOX 4 treatment

Simplified FOLFOX 4 administered IV every 2 weeks:

- Oxaliplatin 85 mg/m² in 2h in 250 mL of G5% (H + 0)
- Folinic acid 400 mg/m² in 2h in 250 mL of G5% (H + 0)
- 5FU 400 mg/m² in 10 min in 100 mL of G5% (H + 2H)
- 5FU 2400 mg/m² as a continuous infusion over 46 hours in G5% in a portable infuser (qsp 230 mL, 5mL/h), pump, or portable syringe pump

**Patients with uni- or bilobar involvement will have chemoembolization and FOLFOX administrations at the following visits:
Or in a bilobar treatment in 2 sessions**

Visit n°	FOLFOX cycle number	Chemoembolization cycle number	Time (days)
1	1		T=0
2	2		T+14
3		1	T+17
4	3		T+28
5	4		T+42
6		2	T+45
7	5		T+56

Either in a unilobar treatment in 4 sessions

Visit n°	FOLFOX cycle number	Chemoembolization cycle number	Time (days)
1	1		T=0
2	2		T+14
3		1	T+17
4	3		T+28
5		2	T+31
6	4		T+42
7		3	T+45
8	5		T+56
9		4	T+59

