- weakly emetogenic
- hematological toxicity

Dose adaptations for guidance only:

Persistent paresthesias between 2 treatments (grade 2)	Reduce oxaliplatin to 65 mg/m ²
Painful paresthesias or with functional discomfort (grade 3)	Stopping oxaliplatin
Dermal toxicity grade > 2	Reduce bolus 5-FU to 300 mg/m ² Reduce continuous 5-FU to 1800 mg/m ² .
Neutropenia < 1000/mm ³ (> grade 2) or thrombocytopenia < 50,000/mm ³ (> grade 2)	Stop bolus 5-FU and reduce oxaliplatin to 65 mg/m ² if thrombocytopenia
Diarrhea, mucositis or other toxicity grade > 2	Reduce oxaliplatin to 65 mg/m ² . Reduce bolus 5-FU to 300 mg/m ² Reduce continuous 5-FU to 1800 mg/m ² .
Grade 3-4 cardiac, cerebellar or allergy toxicity	discontinuation of chemotherapy

Wait for resolution of toxicities in case of grade 3 or 4 before resuming the cycle.

On the day of the resumption of the cycle D1: 1,500 PNN/mm³ and 100,000 platelets/mm³ are needed to resume the cycle.

VI.2 Chemoembolization

The main adverse effects expected with chemoembolization are:

- Unwanted reflux or passage of microbeads into normal arteries adjacent to the targeted lesion or through the lesion to other arteries or arterial beds
- Non-targeted embolization
- Pulmonary embolization
- Capillary bed saturation and tissue damage
- Ischemic stroke or ischemic infarction
- Rupture of a vessel or lesion and hemorrhage
- Neurological deficits including cranial nerve palsy
- Vasospasm
- Repermeabilization
- Foreign body reactions requiring medical intervention
- Infection requiring medical intervention
- Catheter tip clot formation and subsequent mobilization
- Deaths

Expected effects for the embolization procedure (from CNIHM anticancer files November 2008):

- Fever, right upper liver quadrant pain, vomiting
- Transient thrombocytopenia and liver dysfunction
- Increased transaminases (cytolysis)
- Local ischemic and septic manifestations (cholecystitis, hepatic infarction, hepatic abscess, digestive hemorrhage)
- Renal insufficiency

Adaptations for chemoembolization:

- **The chemoembolization procedure will be stopped in case of:**
 - Inability to catheterize the hepatic artery
 - Dissection of the hepatic artery
 - Anaphylactic shock to contrast medium
 - Per-procedural discovery of portal vein occlusion or arteriovenous shunt
 - near-stasis (stop-flow) observed prior to the full dose of irinotecan

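### The cardiac inclusion criterion joins its two negative conditions with *or*; read literally it excludes only patients who have both problems, which contradicts its own heading

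*Protocol*

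**What the plan says.** The inclusion list in Protocol II.1 contains one cardiac item, and the synopsis carries it in the same words. It reads "No cardiac dysfunction", then a colon, then "no cardiovascular events in the past 6 months or no NYHA" ≥ 2. The part before the colon is the heading of the item. The part after it is the rule that a site would apply.

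The list opens with the instruction that "Inclusion in the study requires that all of the inclusion criteria listed below be met". That governs how the bullets combine. It does not say how two conditions inside one bullet combine.

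The non-inclusion list (II.2 and synopsis) has no cardiac item. The nearest is "Known contraindications to 5FU, oxaliplatin, folinic acid, irinotecan or contrast media", which names no cardiac condition. The pre-inclusion assessment (III) asks for medical history and a full clinical examination and names no cardiac test. Patients are entered directly through the eCRF (IV). The SAP restates none of the eligibility criteria.

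**The concern.** The heading promises a patient without cardiac dysfunction, but the rule beneath it can be satisfied by a patient who has it. Someone with a cardiovascular event six weeks ago and NYHA class I passes through the second half. Someone in NYHA class III with no recent event passes through the first.

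The protocol itself shows that cardiac status matters in this trial. The dose-adaptation table in VI.1 lists "Grade 3-4 cardiac, cerebellar or allergy toxicity" as a reason to discontinue chemotherapy. V.2.8 recommends "IV hydration started the day before chemoembolization and continued until day 2, with a 2,000-mL bag per day". Counting the day before, D0, D1 and D2, that is 4 × 2,000 mL = 8 L around each session, with 2 or 4 sessions planned.

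The wording also affects reporting. SAP 7.1.1 counts the patients who met all inclusion criteria, and SAP 5.1.4 restricts the per-protocol population to patients who met the criteria. A rule with two readings gives two answers to both.

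**Working it through.** The plan gives no figure on this point to reproduce. The check is one of logic, followed by tracing the consequence through the SAP.

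**1. Truth table.** Let A be a cardiovascular event in the past 6 months and B be NYHA ≥ 2. The text says (not A) or (not B), which is the same as not (A and B). The heading suggests (not A) and (not B).

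| A: recent event | B: NYHA ≥ 2 | As written | Both conditions required |
|---|---|---|---|
| no | no | qualifies | qualifies |
| no | yes | qualifies | excluded |
| yes | no | qualifies | excluded |
| yes | yes | excluded | excluded |

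As written, 3 of 4 combinations qualify; with both conditions required, 1 of 4 does. The readings differ for exactly two types of patient: those with only A and those with only B. The repeated *no* causes this. A single *no* governing both findings would have made *or* correct.

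**2. Usage elsewhere in the same list.** Where II.1 accepts alternatives it writes *or*: metastases shown by imaging or by histology, primary tumour resected or still in place. Where it wants conditions jointly it writes *and*: the bilirubin, AST, ALT and PAL limits, and the number and size limits for lung nodules. The list's own usage therefore supports the literal reading, while the heading points the other way.

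**3. Consequence in the SAP.** Take a patient with only A or only B who received all planned DEBIRI sessions and met every other criterion.
- Literal reading: eligible in SAP 7.1.1 and in the per-protocol population of 5.1.4.
- Both conditions required: ineligible in 7.1.1 and out of 5.1.4.
- Modified ITT population (5.1.2): no difference, because that set is formed regardless of eligibility.

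The table in SAP section 7 reports the primary endpoint in the per-protocol population too, so that supportive result depends on the reading. The primary analysis set does not.

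**4. Size.** Let a and b be the proportions of candidates with A and with B, and c the proportion with both. The literal rule excludes c. Requiring both conditions excludes a + b − c. The difference is a + b − 2c. The documents give none of the three. Purely assumed values show how far the answer moves:
- a = 5%, b = 10%: 15% with no overlap (c = 0), 14% under independence (c = 0.5%), 5% with full overlap (c = 5%).
- a = 2%, b = 5%: 7%, 6.8% (c = 0.1%) and 3% (c = 2%) respectively.

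These are percentages of candidates, and they assume that every site reads the clause literally. They show that the assumptions determine the result; they are not an estimate for this trial.

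**The case against.** The strongest reply is that the clause explains its heading. To include a patient in NYHA class III, an investigator would have to record "No cardiac dysfunction" for that patient, and many would not. This stands. It means the wording can be read to admit such patients, not that it does so at every site. It does not make the clause sound, because the heading and the rule still disagree.

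Second, the English text is evidently a translation: SAP 4.2 still contains French paragraphs. The wording that sites worked from cannot be seen. That limits confidence about what sites read, but the same wording appears in both the synopsis and II.1, and it is the text under review.

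Third, the contraindication criterion might catch some of these patients, and history and examination are required. The product summaries are in an appendix that is not available here, so neither side can claim this point.

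A reader might go further and infer three things that the documents do not support:
- *That the sponsor meant to admit these patients, or that some were enrolled.* Nothing shows either. The heading suggests the opposite intent.
- *That a stated number of the 58 patients is affected.* The 58 are patients to be included, whereas anyone removed by this criterion is removed among candidates before inclusion. Any such count would also rest on assumed prevalences and an assumed overlap. Independence is doubtful, since the two conditions would be expected to occur together.
- *That early stops and deaths in these patients would feed straight into the primary result.* The modified ITT set requires chemoembolization (first due at D17), at least one chemotherapy cycle and at least one evaluation. A patient who dies before chemoembolization or before any evaluation leaves that set. Stopping treatment is not itself a primary failure (SAP 7.3.1). Such deaths do enter the ITT analysis, and toxicities after a FOLFOX dose enter the tolerance population.

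**Conclusion.** Wrong as written. In both places the rule, followed literally, excludes only patients with both a recent cardiovascular event and NYHA ≥ 2, and so contradicts its heading. This rests on the text and on elementary logic, and needs no numerical assumption.

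The supportable consequence is limited to two things. The wording permits inconsistent eligibility decisions on a criterion that appears intended to protect patients, and it leaves the SAP 7.1.1 count and the per-protocol population open to two readings. The number of patients affected cannot be estimated from the documents. Membership of the primary analysis set is not filtered on this criterion.

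**What to change.** The sponsor should reconcile the clause with its heading in the synopsis and in II.1, using the same wording in both, and state explicitly whether both conditions must be met. Which cardiac rule applies is for the sponsor to decide; no new threshold is proposed here. The two conditions should be captured as separate yes/no eligibility items if the eCRF, which is not among the documents, does not already do so. SAP 7.1.1 and 5.1.4 need no separate rule, because they refer back to the criteria; they should be applied with the clarified reading.

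The cost is one clause corrected in two places and possibly one eCRF change. The downside is that, if both conditions are required, sites that have been reading the wording literally lose a few candidates.

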The patient's inclusion will be done directly via the eCRF; the inclusion confirmation and the inclusion number will be sent to you by email. For any help, the FFCD Randomization - Management - Analysis Center in Dijon is open from Monday to Friday from 9:00 am to 6:00 pm.

After inclusion in the study, treatment should begin within a maximum of 2 weeks.

V. TREATMENT

[figure not shown]
V.1 Treatment scheme:

Bilobar treatment in 2 sessions:

Following this initial treatment plan, all patients will receive FOLFOX chemotherapy every 2 weeks according to the usual schedule until progression or unacceptable toxicity.

Sequential unilobar treatment in 4 sessions:

The chemoembolization treatment can, at the investigator's choice, be administered in a unilobar and sequential manner, in 4 sessions. Thus, the right and left livers will be treated alternately. The administrations of DEBIRI will then be performed at D17, D31, D45, D59 (+/- 2 days), or in case of delayed chemotherapy treatment, 3 days (+/- 2 days) after C2, C3, C4 and C5 of FOLFOX. After this initial treatment plan, all patients will receive FOLFOX chemotherapy every 2 weeks according to the usual schedule until progression or unacceptable toxicity.

V.2 Chemoembolization

V.2.1 Scheduled irinotecan dose

Each vial of DC Bead is loaded with 100 mg of irinotecan. It is intended to use the contents of one vial per lobe. For unilobar disease, there will be 1 vial loaded with 100 mg of irinotecan and for bilobar disease, 2 vials loaded with 200 mg, if the treatment is done in one session.

V.2.2 Microbead size

Microbeads with a size of 100-300 μ m will be used in this study and provided by the sponsor.

V.2.3 Precautions and instructions for loading the medication:

Instructions for loading the beads will be provided in the investigator's binder and the pharmacy bag.

V.2.4 Dilution of the loaded microbeads with a contrast agent

Remove the excess supernatant of the irinotecan solution from the vial containing the loaded microbeads before mixing with the contrast agent. A non-ionic contrast agent should be used. It is recommended that the microbeads be diluted prior to injection with a volume of at least 5-10 mL of contrast agent per mL of microbeads (i.e., 10-20 mL of contrast per vial of microbeads). A good suspension of the microbeads in the contrast must be obtained before administration.

V.2.5 Conservation of loaded microbeads:

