Irinotecan-loaded microbeads can be stored for up to 24 hours in a refrigerator at 2°C to 8°C or for up to 4 hours at room temperature, with or without a non-ionic contrast agent.

V.2.6 Pre-administration assessment:

Prior to each chemoembolization procedure, the patient should be ensured to have adequate liver and hematologic function (total bilirubin \leq 1.5N, ALT, ASAT, and PAL \leq 5N, albumin \geq 2.5g/dL; PNN \geq 1500/mm³, platelets \geq 100,000/mm³, INR $<$ 1.5) and a patent portal trunk.

V.2.7 Procedure

The DEBIRI procedure will begin with a 4 or 5Fr peripheral arterial approach at the operator's convenience.

The operator will first proceed to a diagnostic phase. Successively, he will catheterize the superior mesenteric artery and the celiac trunk. During these angiographies, the operator will identify the disposition of the hepatic arterial vascularization, the permeability of the portal trunk and the vascular topography of the lesions. The operator may be required to perform selective angiography of the phrenic, inferior epigastric, and internal mammary arteries when peripheral hepatic tumors have been identified.

After this diagnostic phase, **lobar administration** will be used whenever possible. The operator will catheterize the right and left hepatic arteries with a maximum 3Fr microcatheter. Prior to DEBIRI injection, the operator will place the microcatheter on the right downstream of the cystic artery, and on the left downstream of the right gastric artery. The right gastric artery may be prophylactically embolized if the operator deems it necessary.

Each vial of irinotecan-loaded microbeads (DEBIRI) will be mixed with at least 10-20 mL of non-ionic iodinated contrast medium (e.g. Imeron 350, Omnipaque 350).

The goal of the procedure is to deliver the entire dose of irinotecan. It is important to maintain anterograde flow in the vessel during the procedure.

DEBIRI should be injected slowly, at a rate of 1 mL of solution per minute.

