When the near stasis point is observed prior to the full dose of irinotecan, the injection of DEBIRI is discontinued regardless of the volume of beads delivered at that time. Therefore, some patients may not receive the entire contents of the prepared vial and may receive a total dose of less than 100 or 200 mg, respectively, in cases of lobar or bilobar involvement. The operator will make sure to respect these recommendations to prevent an inappropriate reflux of DEBIRI that would cause ischemia or necrosis of non-targeted territories.

When the planned dose of irinotecan is administered before the near-stasis point is reached, no additional embolization should be performed with products such as gelfoam, lipiodol or microspheres.

The operator will take care to avoid sedimentation of the beads in the syringe during the procedure by performing gentle rotations or using a three-way valve to keep the beads suspended in the solution.

Extrahepatic vessels may be embolized prophylactically, at the discretion of the interventional radiologist, to minimize extrahepatic infusion of irinotecan beads.

For multifocal or bilobar disease, embolization of each lobe will be performed, at the investigator's discretion, either during the same session or in a unilobar and sequential manner, in 2 sessions. If the treatment is done in one session, the catheter will be placed in the

right and then left hepatic artery and a maximum of one vial of DEBIRI will be administered in each lobe.

Catheter removal and hemostasis at the puncture site will be accomplished by manual compression or by placement of a percutaneous puncture site closure device (e.g., Angioseal™).

Patients will need to be hospitalized overnight following the procedure. After the chemoembolization procedure, vital signs, femoral access point, pain management and hydration will be observed in all patients.

The amount of contrast material delivered to the patient during the procedure, the radiation dose, and the fluoroscopy exposure time should be recorded. The embolized vessels and the amount of embolic agent will be recorded.

All treatments used during the procedure, including analgesic treatments, should be recorded. Any unused irinotecan-loaded microbeads will be discarded.

V.2.8 Peri-chemoembolization treatment recommendations/pre-medication for chemoembolization:

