- If the following grade 3 or 4 toxicities occur as a result of chemoembolization, no additional session will be performed (but FOLFOX will be continued).

- Arteritis
- Grade 3 or 4 hepatic impairment
- Local ischemic and septic manifestations (cholecystitis, hepatic infarction, hepatic abscess, digestive hemorrhage) of grade 3 or 4
- Grade 3 or 4 renal insufficiency
- **The interval between chemoembolization sessions may be extended to allow for recovery of liver function.**
- No dose adjustment of irinotecan is planned for chemoembolization sessions.
- In case of hematological toxicity, FOLFOX dose adjustment rules **will be applied and chemoembolization will be continued.**

In case of doubt, do not hesitate to ask for advice from the study's referring radiologist, [name], through the FFCD.

VII. PATIENT MONITORING DURING TREATMENT AND AFTER WITHDRAWAL OF TREATMENT

Monitoring during treatment:

- **Before each cycle of FOLFOX:**
 - Complete clinical examination including: weight, vital signs, WHO, pain assessment (VAS)
 - Biological check-up: CBC/platelets
 - Adverse event evaluations according to NCI CTC version 4.0
- **Before each chemoembolization session**
 - Complete clinical examination including: weight, vital signs, WHO, pain assessment (VAS)
 - Biological workup consisting of measurements of hematological, nephrological and hepatic parameters: CBC/platelets, blood ionogram, creatinine, albumin, transaminases (AST, ALT), alkaline phosphatases (ALP), total and conjugated bilirubin, PT
 - Adverse event evaluations according to NCI CTC version 4.0

CEA and CA 19-9 assays, as well as thoracoabdomino-pelvic CT and liver MRI will be performed at an initial evaluation between D63 and D70 and then every 2 months after the start of treatment.

For patients participating in the associated 'lipid' translational study, please remember to perform the fasting sample and then technician the sample.

After the chemoembolization treatment period:

All patients will receive chemotherapy with FOLFOX every 2 weeks according to the usual regimen until progression or unacceptable toxicity.

VIII. STOP PROCESSING THE STUDY

The processing of the study will be stopped in case of:

- Investigator's decision
- Major toxicity requiring discontinuation of treatment (despite protocol adaptations)
- Serious or unexpected event requiring discontinuation of protocol treatment
- Progression of the disease
- Patient refusal or withdrawal of consent

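### Cheap improvement: no liver or renal chemistry is scheduled after the last DEBIRI session or, in the 2-session plan, for a nominal 28 days after session 1, so asymptomatic grade 3-4 values may go unmeasured

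*Protocol*

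**What the plan says.** **Baseline.** Protocol III requires a full hematological, renal and hepatic panel within 14 days before inclusion, including "alkaline phosphatases (ALP), total and conjugated bilirubin, PT, APTT, fibrinogen level".

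**During treatment.** Protocol VII gives two lists. Before each FOLFOX cycle there is a clinical examination, CTC grading and one laboratory entry, "Biological check-up: CBC/platelets". Before each DEBIRI session the laboratory list is longer: CBC, ionogram, creatinine, albumin, AST, ALT, ALP, total and conjugated bilirubin, and PT. Protocol V.2.6 supports the second list: "Prior to each chemoembolization procedure, the patient should be ensured to have adequate liver and hematologic function". It sets limits for bilirubin, transaminases, ALP, albumin, neutrophils, platelets and INR.

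**After a session.** Protocol V.2.7 states: "Patients will need to be hospitalized overnight following the procedure". It then states: "After the chemoembolization procedure, vital signs, femoral access point, pain management and hydration will be observed in all patients". No laboratory test is named. Protocol V.2.8 recommends renal prophylaxis, "IV hydration started the day before chemoembolization and continued until day 2", without a creatinine check afterwards. The evaluation at D63-D70 and those that follow name CEA, CA 19-9, CT and liver MRI.

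**Expected toxicity and its consequence.** Protocol VI.2 lists transient liver dysfunction, raised transaminases and renal insufficiency as expected effects of embolization. It bars further sessions if grade 3 or 4 hepatic impairment or renal insufficiency results from a session.

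**Reporting.** Tolerance is a secondary criterion. SAP 7.5.3 counts toxicities by type and maximum grade. Protocol XII.4 adds a Kaplan-Meier estimate of time to grade 3/4/5 toxicity.

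**The concern.** The protocol expects liver and kidney effects from embolization and describes the liver effect as transient. Yet the tests that would show them are scheduled only just before the next embolization. A transient effect can rise and resolve between two such tests, and after the last session there is no next test. A raised creatinine or ALT without symptoms cannot be graded by clinical examination and a blood count.

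Two things are at stake:

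- **Ascertainment.** A patient whose abnormal value was never measured counts as event-free in the maximum-grade tables and in the time-to-toxicity estimate. Protocol XII.5 plans an early committee review of SAEs, and an asymptomatic value need not be an SAE.
- **The bar on further sessions.** A grade 3-4 event after one session that resolves before the next panel would leave the bar unapplied, if a resolved value counts under it. VI.2 does not say whether it does.

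**Working it through.** No sample-size or test calculation applies. The check is schedule arithmetic on the two visit tables in Protocol V.3, introduced by "Patients with uni- or bilobar involvement will have chemoembolization and FOLFOX administrations at the following visits".

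**Inputs**
- FOLFOX C1 to C5: T=0, T+14, T+28, T+42, T+56. C6 is extrapolated at the 2-week interval: 56 + 14 = 70.
- DEBIRI, 2-session plan: T+17, T+45.
- DEBIRI, 4-session plan: T+17, T+31, T+45, T+59. Protocol V.1 allows +/- 2 days on these dates or, if chemotherapy is delayed, "3 days (+/- 2 days) after C2, C3, C4 and C5 of FOLFOX".
- Patients to be included: 58 (Protocol XII.3).

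**Interval between sessions, each preceded by a required panel**
- 2-session plan: 45 - 17 = 28 days. The FOLFOX visits inside it, D28 and D42, require only CBC/platelets.
- 4-session plan: 31 - 17 = 45 - 31 = 59 - 45 = 14 days. If one session is 2 days early and the next 2 days late, 14 + 2 + 2 = 18 days.
- These are nominal figures, not maxima. VI.2 lets the interval be extended for recovery of liver function, and a delayed cycle moves the session. The gap is shorter if the panel is drawn some days ahead; VII does not say how far ahead it may be drawn.

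**After the last session**
- The last session is at D45 or D59. The D63-D70 evaluation falls 63 - 45 = 18 to 70 - 45 = 25 days later in the 2-session plan, and 63 - 59 = 4 to 70 - 59 = 11 days later in the 4-session plan. It names no liver or renal chemistry, and neither do the later evaluations or FOLFOX cycles.

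**First FOLFOX blood sample after each session**
- 2-session plan: 28 - 17 = 11 and 56 - 45 = 11 days.
- 4-session plan: 28 - 17 = 42 - 31 = 56 - 45 = 70 - 59 = 11 days, or 9 to 13 with the +/- 2 days on the session.

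Chemistry added to the FOLFOX-day blood would therefore bring the first test after session 1 of the 2-session plan from a nominal 28 days to 11. It would also give a test after the last session, where none is now scheduled.

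**Panels added, from C3 through the first cycle after the last session**
- 2-session plan: C3, C4, C5 = 3 per patient; 58 x 3 = 174.
- 4-session plan: C3, C4, C5, C6 = 4 per patient; 58 x 4 = 232.

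Both totals assume that all 58 patients complete every session. A mix of the two plans lies between them.

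**The case against.** **Patients are still monitored.** This is correct. D28 and D42 each include an examination, a blood count and CTC grading, and Protocol X collects events between visits. A reader might infer that patients are unmonitored after embolization; the documents do not support that. What remains is the narrow class of values that cause no symptoms.

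**Protocol X refers to biological status at scheduled visits.** It names no assay, and VII is the specific schedule. Investigators may test in routine care, but the readable text does not require it, so practice could differ between centers.

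**The bar on further sessions still works.** It does for abnormalities that persist, renal as well as hepatic, because the pre-session panel includes creatinine. The option to lengthen the interval for liver recovery also suggests that treating after recovery is partly foreseen. A reader might infer that the bar cannot operate; only its application to a resolved event is in doubt.

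**The SAP covers this elsewhere.** SAP 7.5.1 reports causes of missed and deferred sessions, which would capture toxicity that stops or delays treatment. Laboratory grades belong in 7.5.3, so their absence from 7.5.1 is no gap. The time-to-toxicity estimate appears in Protocol XII.4 but is not repeated in SAP 7.5.3. These points limit the consequence, but neither section can report a value that was never measured.

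**The remedy is partial.** A sample at about day 11 misses earlier peaks, and FOLFOX cycles after the last added sample again carry no chemistry. Both points stand.

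**The FOLFOX-day sample could replace the pre-session panel.** This saving is tempting but unsound. The five added assays lack the albumin and INR that V.2.6 needs and the ionogram, conjugated bilirubin and PT that VII lists. That blood is also drawn before the FOLFOX dose, so its counts would not reflect that cycle.

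**Conclusion.** The gap is real on the readable text. After the last DEBIRI session, and for a nominal 28 days after session 1 of the 2-session plan, no liver or renal chemistry is scheduled. In the 4-session plan the between-session interval is nominally 14 days, up to 18 within the date windows. Either interval is longer if a session is delayed.

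The consequence is limited to possible under-counting of asymptomatic grade 3-4 laboratory toxicity in a descriptive secondary objective and, depending on how VI.2 is read, a bar on further sessions that is not applied. The documents give no incidence of such events and no rate of unscheduled testing, so the size of any under-count cannot be computed. A reader might take the gap as evidence that the reported toxicity will be materially wrong; nothing in the documents shows that. The primary endpoint and its decision rule are untouched.

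The conclusion assumes that no laboratory schedule stands in the treatment-scheme figures, appendices, Investigator's Brochure or eCRF, none of which were available here. Severity: optional to minor.

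**What to change.** - **Protocol VII:** add AST, ALT, ALP, total bilirubin and creatinine to the blood already drawn before each FOLFOX cycle, from C3 through the first cycle after the last DEBIRI session (D56 in the 2-session plan, about D70 in the 4-session plan). Keep the full pre-session panel unchanged, including albumin, PT/INR, ionogram and CBC, and state that the FOLFOX-day sample does not replace it.
- **SAP 7.5.3:** report hepatic and renal laboratory grades together with the number of patients who have post-session values, so that untested patients are visible.
- **Optional:** draw the same five assays before discharge from the overnight stay, to catch early peaks (58 x 2 = 116 or 58 x 4 = 232 samples). A sentence in VI.2 on whether a resolved grade 3-4 value bars the next session would settle that reading.

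**Cost:** 3 added panels per patient in the 2-session plan or 4 in the 4-session plan, some eCRF fields, and no new visit. Reported laboratory toxicity may be higher, which reflects better measurement. Without the discharge sample, peaks that resolve before about day 11 are still missed.
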